### **III. Subject Participation**

#### **A. Recruitment:**

1. Participants will be recruited through clinic, community-based efforts, and social media platforms. Flyers will be placed around Swope and KUMC for patients to take. We will use the KUMC HERON database and the TMC electronic medical records to identify smokers and will ask their physician to send their patient a letter informing them of the study. We will also use the Frontiers registry to identify adult smokers who have agreed to be contacted for research. We will also use radio ads, word of mouth, and our existing pool of participants from prior studies. We will post the study to the KUMC Intranet list of current studies for KUMC employees. Additionally, participants are currently being screened for other research studies conducted by our team. Those who have completed studies or who are ineligible for other studies being conducted will be informed about the current study and offered the

opportunity to be screened. Recruitment letters, advertisements, and flyers are in the process of being developed. They will be submitted to the IRB for approval before any participants are enrolled.

2. Recruitment methods are described above. Recruitment will be conducted by members of the study team. Recruitment will be overseen by Drs. [name] and [name]. Screening will be conducted over the phone.
3. Advertisements and flyers that will be used for recruitment are attached. Advertisements and flyers will be handed out to potential participants by the study team and will be placed in clinics at Swope and KUMC.

**B. Screening Interview/questionnaire:** The screening will be conducted over the phone. The screening questionnaire will address the general inclusion/exclusion criteria as listed above. Only participants who have expressed interest will be screened. Prior to screening, participants will be given a brief overview of the study and informed that we need to collect some information to learn whether they may be eligible for the research. They will be informed that completion of the screening interview is voluntary, and they can discontinue screening at any time. Participants will be asked to provide verbal consent for screening.

**C. Informed consent process and timing of obtaining of consent**

- 1 Consent procedures will be conducted by trained members of the research team. Prior to consent, participants will be provided a detailed and comprehensive overview of study procedures.
- 2 Individuals interested in the proposed study will meet the research assistant at the Fairway CRU. Each individual will be given a copy of the consent form and as much time as they need to review its contents. After the consent form is read, both the individual and the research assistant will review the consent form together and the potential participant will be encouraged to ask questions. Each individual will be reminded that participation in the study is completely voluntary. The consenting process will take place in a private location.
- 3 We are recruiting otherwise healthy smokers and do not anticipate recruitment of subjects with compromised cognitive abilities and/or decisional impairment. However, if questions regarding a participant's ability to provide informed consent arise, Drs. [name] and [name] will determine whether the subject is able to give informed consent.

**D. Alternatives to Participation:** The alternative to participation is not participating.

**E. Costs to Subjects:** There are no costs to participants. All tests, procedures, and visits are being performed solely for research purposes and are not billable to insurance companies.

**F. How new information will be conveyed to the study subject and how it will be documented:** We have plans to publish data from this study in aggregate but will not provide any individualized feedback to patients.

**G. Payment, including a prorated plan for payment:** Participants who screen fail at visit one will be compensated \$20 and will not be allowed to continue with the study. Eligible participants who complete study procedures will receive \$50 for visit one, \$75 for visit two, \$100 for visit three, and \$50 for visit four (if

participant qualifies) in appreciation for their time and participation. Participants may receive an addition \$50 at visit three if they attend all visits, return completed practice logs, and have CO  $\leq$  12 ppm at all visits. For each visit that must be rescheduled due to CO  $>$  12 ppm or an incomplete practice log, participants will have \$10 deducted from their bonus. Finally, participants will be provided transportation via a rideshare service to and from each visit.

#### **H. Payment for a research-related injury:** N/A

### **IV. Data Collection and Protection**

**A. Data Management and Security:** Confidentiality will be maintained by assigning each participant a study identification number and numerically coding all data. The association of the ID-code and the participant's name will be kept by [name] in a locked file cabinet. The screening questionnaire and all survey data will be directly entered into RedCap or CRIS and accessible only by study staff. Any paper copies of records will be kept in a locked filing cabinet in offices that are kept locked when unoccupied. Only summaries of group data will be reported in any publications or presentations, with no identification of individuals. Because identifiable information will be collected, participant privacy will be maintained throughout the duration of the study by adhering to the regulations set forth by the HIPAA Privacy Rule. More specifically, identifiable information will not be released without written authorization of the participant. Mobile devices will not be used for data collection or storage. Identifiable data will not be sent outside of KUMC.

**B. Sample / Specimen Collection:** No more than 7 mL of blood will be collected per blood draw (7 mL per draw x 5 draws per visit x 3 visits = 105 mL total during study). All samples will be de-identified and labeled with a study identification number. Blood samples will be aliquoted into two separate vials. One will be analyzed for the current study and one will be placed in a biospecimen repository if participant provides consent for biorepository. Participants will complete no more than two study visits in a seven-day period. Samples will be stored at the Bioanalytical Laboratory at the Fairway Clinical Research Center under the direction of [name]. Samples will be accessible only to members of the study team. Results from biomarker analyses will be de-identified and shared only with members of the research team. Any resulting publications will present the data in aggregate; individual participants will not be identified. Samples will be disposed of one month after the final report is sent out to the Principal Investigator, unless participants agree to have their samples stored for future testing. For participants who agree to future testing, samples will be stored indefinitely.

**C. Tissue Banking Considerations:** For participants who agree to future testing, samples will be stored indefinitely. New markers of nicotine and carcinogen exposure and genetic differences in nicotine metabolism are being discovered and the stored biological samples would be used for analysis of these new markers. All samples stored for future biomarker analyses will be de-identified and accessible only to members of the study team. Results from these analyses will be de-identified and shared only with members of the research team. Any resulting publications will present the data in aggregate; individual participants will not be identified.

**D. Procedures to protect subject confidentiality:** Confidentiality will be maintained by assigning each participant a study identification number and numerically coding all data. All biological samples and survey data will be labeled with the study identification number and never with the participant's name or other identifiable information. The association of the ID-code and the participant's name will be kept by [name] in a locked file cabinet and will only be accessible to members of the study team.

**E. Quality Assurance / Monitoring:** All data will be directly entered into our electronic data capture system (i.e., RedCap or CRIS) that contains edit checks to control the quality and completeness of data entry. Completeness of data entry will be automatically verified before each assessment is completed. The electronic data capture system is behind the KUMC secure firewall with role-based access that is HIPAA and human subjects compliant. There are no plans for ongoing third-party monitoring.

#### **V. Data Analysis and Reporting**

**A. Statistical and Data Analysis:** See section II.C. above for sample size and power calculations. To determine differences on self-report measures between products, an analysis of variance (ANOVA) will be conducted. Differences in nicotine delivery will be compared across products at each timepoint using similar procedures. Mean differences in puff allocation will be investigated for the computer task.

**B. Outcome:** The primary study endpoint is nicotine delivery. We hypothesize that combustible cigarettes will show the fastest and greatest nicotine delivery, followed by e-cigarettes, and heat-not-burn devices. Further, topography measures will be greatest for cigarettes, followed by e-cigarettes, and heat-not-burn devices. In terms of self report measures of abuse liability, use of cigarettes will be associated with the greatest reduction in symptoms of nicotine withdrawal and craving. Exhaled carbon monoxide will be greatest for cigarettes, followed by heat-not-burn devices and e-cigarettes (no exposure). The primary endpoint of the computerized concurrent choice task is the proportion of puffs allocated to each product. The third aim is exploratory, and we therefore do not have specific hypotheses related to aim three.

**C. Study results to participants:** Study results will not be shared with research participants.

**D. Publication Plan:** We plan to publish results in appropriate tobacco and public health journals such as Addiction, Tobacco Control, Nicotine and Tobacco Research, etc. In addition, results will be presented at regional, national, and international conferences.

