**I. Purpose, Background and Rationale**

**A. Aim and Hypotheses**

1. Use of electronic cigarette (e-cigarette) and heat-not-burn (HNB) products is continuing to proliferate in the US. In fact, e-cigarette use is expected to surpass combustible cigarette smoking rates in the next two years. The US FDA has regulatory authority to set appropriate product standards for e-cigarettes and heat-not-burn products with the goal of maximizing public health. Initial data suggest that these products present reduced harm compared to combustible cigarette smoking, but the comparative abuse liability and interest in use by smokers, particularly as a function of product flavor, remains largely unknown. These questions are critical in helping the FDA impose meaningful and effective regulations on these products. African American (AA) smokers are showing increased interest in these new and emerging products. Research suggests AA smokers take larger puffs and inhale more deeply than whites. Therefore, data are needed to understand if AA smokers will also use e-cigarettes and HNB devices in such a way that could inadvertently increase harm in the long run. Additionally, research is urgently needed to understand whether these products (if shown to be less harmful than cigarettes), would be an acceptable alternative to traditional smoking and how product flavor (tobacco vs. menthol) impacts use patterns and preference. The current study is not a cessation study and does not aim to induce long-term uptake of the study products. The objective of the study is to test the acute pharmacokinetic profile of these products during a 65-minute use period with each product across three to four study visits.

2. Aim 1: Understand the abuse liability of heat-not-burn devices, e-cigarettes, and combustible cigarettes in terms of nicotine delivery, puff patterns (topography), and reductions in nicotine withdrawal/craving. H1: Combustible cigarettes will show the fastest and greatest nicotine delivery, followed by e-cigarettes, and heat-not-burn devices. H2: Topography measures will be greatest for cigarettes, followed by e-cigarettes, and heat-not-burn devices. H3: Use of cigarettes will be associated with the greatest reduction in symptoms of nicotine withdrawal and craving.

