**C. Sample size, statistical methods, and power calculation**

1. 20 eligible AA and white smokers will be randomized. We will use a 1:1 fashion randomization to product order (combustible cigarette, e-cigarette, heat-not-burn device vs. combustible cigarette, heat-not-burn device, e-cigarette). Randomization will be determined by computer-generated random numbers. Randomization assignments will be placed in sealed envelopes with sequential study ID numbers. After baseline data collection has been completed, the research assistant will select the sequential study ID number to determine the randomization assignment
2. No blinding is involved in the first three study visits. For participants who complete the fourth visit (flavor assessment), participants and research assistants that interact with participants will be blind to flavor (double blind design).
3. Due to the pilot nature of the current study, a primary aim of the study is to collect data for power calculations for a fully powered trial. Therefore, formal power calculations were not conducted. ANOVAs will be conducted to detect within-subject differences between products for all outcomes. A Bonferroni correction will be applied to adjust for multiple comparisons. A paired samples t-test will be conducted to detect differences in outcomes in the e-cigarette flavor assessment.

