#### **A. E. Specific methods and techniques used throughout the study**

1. Laboratory tests: Throughout each visit, blood will be collected for nicotine analysis via an IV catheter placed in the patient's arm. Blood draws will occur during the PK phase of each visit and will be taken at baseline (0 minutes), 5 minutes, 7 minutes, 15 minutes, and post-ad lib portion (may vary by participant depending on how long they choose to use the product). No more than 7 mL of blood will be drawn per draw ( $\leq 35$  mL per visit). Blood will be processed and analyzed for nicotine and cotinine levels. If consent is provided for banking, samples will be banked for possible future analysis.
2. Study Procedures:
  - a. **Initial screening:** The initial screening will review inclusion/exclusion criteria. Those eligible will be scheduled to completely visit within 14 days.

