  - b. **Visit one:** At visit one, participants will be re-screened according to inclusion/exclusion criteria. They will be instructed to remain nicotine abstinent for 12 hours prior to the visit. Participants will complete carbon monoxide (CO) measurement to confirm abstinence ( $CO \leq 12$  ppm). CO is collected by a simple, non-invasive breath test that involves the participant holding their breath for  $\sim 15$  seconds and then exhaling into a straw connected to the CO monitor. Participants will be provided with an overview of the study, will provide informed consent, and complete baseline self-report measures. Participants will then complete the PK phase of the study. Participants will have an intravenous catheter placed in their arm. They will complete a 10-puff standardized puffing bout followed by a 60-minute ad-lib smoking session with their usual brand cigarette. Specifically, a research assistant with a stopwatch will instruct the participant to take a puff every 30 seconds, resulting in 10 puffs over 5 minutes. Throughout the session, puff topography will be measured via a pressure sensor attached to the device/product. This will not require anything additional of the participant. Blood draws will occur during the 10-puff bout at -5, 5, 7, 15, and at the end of the ad-lib smoking period ( $\sim 60$  minutes after the 10-puff bout). Following the smoking period, the participant will be instructed to make notes regarding their preferences related to the product (e.g., liking, satisfaction, craving, intentions/willingness for future use). Participants will complete self-report measures of nicotine craving and withdrawal at each blood draw during the 10-puff bout and every 10 minutes throughout the ad-lib smoking period. At the end of the session, participants will complete a measure of product liking/evaluation. At the end of visit one, participants will be randomized to product order (e-cigarettes followed by HNB device vs. HNB device followed by e-cigarette). Participants will be shown how to use the device, puff on it, charge it, replace the pod/heat stick. Participants will be compensated \$50 for this visit.

[figure not shown]
addition, participants will be asked to bring an unopened pack of their usual brand cigarettes to this visit. They will be compensated an additional \$6 for this, bringing their total compensation to \$56 for this visit. We anticipate the visit to last no more than 3 hours.

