**Computer screen simulation for task:**

[figure not shown]
g. Visit four (menthol smokers only): Participants who report typically smoking menthol cigarettes will be invited to complete a fourth session. Participants will undergo overnight tobacco/nicotine abstinence before the visit ( $eCO \leq 12 \text{ ppm}$ ). Participants will then be randomized 1:1 to e-cigarette flavor order (tobacco e-cigarette, menthol e-cigarette). They will complete a 30-minute ad libitum session with the first product, based on randomization, followed by a 1.5 hour standard washout period, followed by a 30-minute ad libitum vaping session with the second product. Throughout each session, puff topography will be measured via a pressure sensor attached to the e-cigarette device. Participants will complete self-report measures of smoking urges and withdrawal symptoms pre- and post-vaping session. In addition, they will complete measures of subjective vaping experience, perceptions of flavor, product demand, and intentions for

future use. We anticipate that the session will last ~3 hours.

Participants will earn \$50 for attending the study visit.

h. **Six-month follow-up:** Six months after completion of visit 3 (or study discontinuation), participants will be contacted by phone to assess ongoing use of study products. Three attempts will be made to contact the participant for this follow-up. If they endorse ongoing use, they will be advised to quit all tobacco use and offered a referral to the Quitline. We anticipate this phone follow-up to last no more than 10 minutes. This follow-up assessment is for safety monitoring only.

3. Due to COVID-19 and the need to keep patients and researchers safe, we will use Zoom, a HIPAA compliant, university approved video conferencing software, during the visit. This will allow the participant to smoke freely (unmasked) while the researcher can watch and communicate with the participant via video conferencing from outside the clinic room. We will utilize Zoom as much as possible and only enter the room when absolutely necessary.
4. All tests, procedures, and visits are being performed solely for research purposes and are not billable to insurance companies.

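### The plan does not say how the H3 reduction in craving and withdrawal is formed, and it gives the same-session pre-use score no role in the analysis

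*Combined protocol and SAP*

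**What the plan says.** Section I.A, Aim 1, H3: "Use of cigarettes will be associated with the greatest reduction in symptoms of nicotine withdrawal and craving". Section V.B repeats this as an expected outcome: "use of cigarettes will be associated with the greatest reduction in symptoms of nicotine withdrawal and craving". Neither place defines the reduction, its reference time or its end time.

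The analysis text is short. Section V.A: "To determine differences on self-report measures between products, an analysis of variance (ANOVA) will be conducted". Section II.C: "ANOVAs will be conducted to detect within-subject differences between products for all outcomes". II.C also applies a Bonferroni correction, without stating alpha or the number of comparisons, and assigns a paired t-test to the visit 4 flavor comparison.

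The pre-use score exists. Section II.E, visit one: "Participants will complete self-report measures of nicotine craving and withdrawal at each blood draw during the 10-puff bout", and in the same paragraph "Blood draws will occur during the 10-puff bout at -5, 5, 7, 15, and at the end of the ad-lib smoking period". Scoring continues every 10 minutes in the ad-lib period, and visits 2 and 3 repeat the same session. The laboratory-tests paragraph of II.E labels the draws differently: they "will be taken at baseline (0 minutes), 5 minutes, 7 minutes, 15 minutes". For the flavor visit: "Participants will complete self-report measures of smoking urges and withdrawal symptoms pre- and post-vaping session".

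**The concern.** A reduction is a difference between two scores from the same session. The plan names the reduction as what it expects to see and collects both scores, but then describes an analysis of the measures without connecting them. Each session also yields several scores after use begins, and the plan does not say which of them is tested.

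This would matter little if every session started at the same level in expectation. For the contrasts that H3 makes, the design does not secure that. Under II.C the cigarette comes first in both sequences, and only the order of the e-cigarette and the heat-not-burn (HNB) device is randomized. Under II.E.2 each device visit follows about two to five days of home practice in which participants are urged to replace their cigarettes; the cigarette visit has no such run-in. Starting craving at the cigarette visit could therefore differ systematically from that at the device visits. A comparison of levels would mix that difference with relief, and could create or hide an apparent product effect.

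**Working it through.** The plan states no power, alpha, effect size or SD for craving or withdrawal, so there is no figure to reproduce. What follows is illustration.

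**Inputs from the documents:** n = 20 (II.C); three products, cigarette always first (II.C); pre-use score at -5 minutes (II.E, visit one).

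**Assumed inputs:** a paired contrast of two products; two-sided alpha of 0.05, or 0.05/3 for three pairwise comparisons; the SD of the between-product difference in post-use score set to 1, and the same for the pre-use score; rho, the correlation between those pre-use and post-use differences, from 0 to 0.7; any pre-use shift carried fully into the post-use score.

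**1. What each analysis estimates.** Assume a 0-100 scale, with pre-use means of 80 and 65 and a fall of 40 with both products. Post-use means are 40 and 25.
- Post-use level: 40 - 25 = 15.
- Change: (80 - 40) - (65 - 25) = 0.
- Pre-use score as covariate with slope b: 15 - 15b, which is 7.5 at b = 0.5 and 4.5 at b = 0.7.

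H3 is worded as a reduction, so the change score is the version that matches it. The covariate version gives the same product contrast whether the response is change or post-use score. It returns 0 here only if b = 1.

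**2. Effect on the test.** Equal true reductions, paired t-test, n = 20, noncentral t with noncentrality shift × sqrt(20):

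| Pre-use shift (SD) | Post-use only, alpha 0.05/3 | Post-use only, alpha 0.05 |
|---|---|---|
| 0.25 | 0.09 | 0.19 |
| 0.50 | 0.37 | 0.57 |
| 0.75 | 0.76 | 0.89 |

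The change score stays at nominal alpha in every row. A shift in the other direction hides effects. Suppose the true difference in reduction is the 0.78 SD that gives the post-use comparison 80% power at 0.05/3. An opposing shift of 0.25 or 0.5 SD lowers that power to 0.43 or 0.11.

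**3. Precision with no pre-use shift.** The SD is 1 for post-use, sqrt(2(1 - rho)) for change and sqrt(1 - rho²) for covariate adjustment (one degree of freedom fewer). Power at 0.78 SD, alpha 0.05/3:

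| rho | Post-use | Change | Covariate |
|---|---|---|---|
| 0 | 0.80 | 0.46 | 0.80 |
| 0.3 | 0.80 | 0.63 | 0.84 |
| 0.5 | 0.80 | 0.80 | 0.91 |
| 0.7 | 0.80 | 0.96 | 0.98 |

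In large-sample terms, covariate adjustment cuts the SE by 1 - sqrt(0.75) = 13% at rho 0.5 and 1 - sqrt(0.51) = 29% at rho 0.7. That is equivalent to 20/0.75 = 26.7 and 20/0.51 = 39.2 participants.

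**4. Those gains need balanced pre-use means.** In a simulation of 20 paired differences with a 0.5 SD pre-use shift, the covariate-adjusted SE relative to the post-use SE was 1.01 at rho 0.5 and 0.83 at rho 0.7. The remaining bias was 0.25 and 0.15 SD. With a 1 SD shift the SE ratios were about 1.3 and 1.07, worse than no adjustment. The change score had no bias in either case.

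**The case against.** The strongest reply is that the plan nowhere says that raw post-use levels will be compared. II.C applies ANOVA to all outcomes, and V.B describes the self-report outcome as a reduction, so an ANOVA of change may be what is intended. This stands: a reader might infer from V.A that the sponsor has chosen a level comparison and that H3 will be decided by starting craving, but the documents are silent on that choice. The defect is missing specification.

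Second, participants arrive after 12 hours without nicotine, checked by exhaled CO at each product visit, and the two devices share the same practice period and have randomized order. This also stands in part. It leaves e-cigarette versus HNB balanced in expectation and confines the concern to cigarette-versus-device contrasts. It does not settle those. Equal abstinence does not guarantee equal craving after different run-ins, and by the plan's own expectation e-cigarettes produce no CO exposure, so the CO check is not informative about e-cigarette use.

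Third, a reader might extend the bias argument to visit 4, where the second session starts 1.5 hours after vaping. The documents do not support that. Flavor order is randomized 1:1, so a lower second start falls on both flavors equally in expectation, and H3 does not cover that visit. Only precision and chance imbalance are at issue there.

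Fourth, a reader might expect covariate adjustment to remove the bias and deliver the full precision gain together. Steps 1 and 4 of the working show that it does not.

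Finally, this is an unpowered pilot whose primary endpoint is nicotine delivery. That limits the consequence. It does not remove it, because the pilot is meant to supply inputs for the power calculation of a larger trial, and an undefined H3 outcome supplies an undefined effect and variance.

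**Conclusion.** The concern holds as a gap in specification. H3 is about change, the pre-use score is collected in every product session, and neither V.A nor II.C says how the reduction is formed, at what time, or what role the pre-use score has. If levels were analyzed, the cigarette-versus-device contrasts would carry any pre-use difference in full. The rejection rates in the working show that this could be large with 20 participants, but the shifts, rho, alpha and number of comparisons are all assumptions, and the documents give neither the size nor the direction of any actual difference. The precision figures apply only where mean pre-use scores are balanced. The consequence is moderate: this should be corrected, but it does not affect the primary endpoint.

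**What to change.** - In V.A, define the H3 outcome as change from the same session's pre-use score to one stated time point. Test it in the within-subject product model, or as a product-by-time effect with the pre-use time included.
- Report alongside it the version with the same-session pre-use score as covariate. It is useful mainly for e-cigarette versus HNB and for visit 4 urges and withdrawal, where order is randomized and the gain is precision.
- Report mean pre-use scores by product and visit, so that readers can see whether starting levels differed.
- Reconcile the label of the pre-use time in II.E (0 minutes in one paragraph, -5 in another) when defining it.

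The cost is wording only, since the scores are already scheduled. There is a statistical price: a plain change score is less precise than the post-use score when rho is below 0.5, and the covariate uses one degree of freedom. None of this separates cigarette from visit 1. That confounding is in the design and should be stated as a limitation of the cigarette-versus-device results.
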